#### 10.3.1. Disposition of the Study Subjects

The disposition of subjects will be described with summaries by treatment group of the number of subjects in each analysis set described above, the number of subjects who completed the study, and the

number of subjects for whom study drug was permanently discontinued (including the reasons for discontinuation). Randomized set will be used to produce this analysis.

### **10.3.2. Demographic and Baseline Characteristics**

Demographic and Baseline characteristics will be summarized and compared by treatment group. Results will be reported using subjects in the randomized, full analysis, per protocol and PK analysis sets.

Prior and concomitant medications will be classified according to the anatomical therapeutic chemical codes in the WHO Drug dictionary. The incidence rate of each coded medication will be tabulated by treatment group. The table will be sorted by the incidence use of the entire sample.

### **10.3.3. Exposure to Study Treatment and Compliance**

Frequency distributions of the number of doses received will be presented by treatment group. Treatment duration and treatment compliance for all randomized subjects will also be described by treatment group.

### **10.3.4. Analysis of Primary Efficacy Endpoints**

The primary efficacy endpoint is the proportion of subjects with HBV DNA <LLOQ at Week 48.

The proportion of subjects achieving the primary efficacy endpoint will be reported along with the corresponding 95% asymptotic confidence interval by treatment group. The proportion of responders will be compared between the 2 treatment groups using a *Cochran-Mantel-Haenszel* test accounting for stratification factors.

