**Exploratory Endpoints:**

- Proportion of subjects with loss of serum viral antigens (defined as <LLOQ) in HBeAg, HBcrAg, and HBsAg
- Proportion of subjects with HBeAg seroconversion (defined as loss of HBeAg and appearance of HBeAg antibody [HBeAb]) or HBsAg seroconversion (defined as loss of HBsAg and appearance of HBsAg antibody [HBsAb]) at each timepoint
- Immunologic outcomes, including changes in humoral and cellular immunity to PBO+NrtI and ABI-H0731+NrtI
- Pharmacogenomic correlations may be performed with clinical or virologic outcomes for subjects who provide optional informed consent
- For subjects who provide an optional pharmacogenomic sample, to evaluate known gene variants and ABI-H0731, its metabolites, and PK and/or safety

**Statistical  
Methods:**

This is a proof-of-concept study. The sample size is similar to that previously utilized for this type of study and is not based upon statistical considerations.

All safety, antiviral activity, and PK endpoints will be summarized using descriptive statistics by dose groups within cohorts. Continuous endpoints will be described using the mean, standard deviation, median, minimum, and maximum. Categorical endpoints will be described using the number and percent of subjects who meet the endpoint criterion.

Due to sample size limitations, no formal statistical inference is planned. Assessment of antiviral activity will be compared by treatment groups using 95% confidence intervals where appropriate.

**Key  
Eligibility  
Criteria:****Inclusion Criteria:**

Subjects must meet all the following inclusion criteria in order to be eligible for the study:

1. Willing and able to provide informed consent
2. Male or female between the ages 18 and 65 years (inclusive)
3. Body mass index (BMI) 18 to 36 kg/m^2 and a minimum body weight of 45 kg (inclusive)
4. Female subjects of child-bearing potential ([Appendix 4](#)) must be non-pregnant and have a negative serum pregnancy test at Screening and a negative urine pregnancy test predose on Day 1
5. HBeAg positive or HBeAg negative CHB, defined as HBV infection documented for  $\geq 12$  months

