## **6. INVESTIGATIONAL MEDICAL PRODUCTS**

### **6.1. Randomization, Blinding and Treatment Codes**

#### **6.1.1. Randomization**

Randomization of eligible subjects to their respective treatment assignments will be performed centrally using an Interactive Response Technology (IRT) system. Following successful completion of Screening assessments and confirmation of subject eligibility, site personnel will enter the subject specific information in the IRT system and receive a subject number at the Screening visit. Upon confirmation of subject eligibility on Day 1, the IRT system will assign eligible subjects in a 1:1 ratio to receive either 300 mg ABI-H0731+NrtI for 96 weeks (n=20) or PBO+NrtI for 48 weeks followed by 300 mg ABI-H0731+NrtI for 48 weeks (n=20). Individual treatment assignments will be stratified by the concurrent NrtI administered (ie, ETV versus TDF or TAF) and HBV DNA (HBV DNA  $\geq$ 500 IU/mL versus <500 IU/mL). The study will enroll approximately 75% subjects receiving ETV. Additional information on the use of the IRT is provided in the IRT user manual.

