### **10.3.5. Analysis of Secondary Efficacy Endpoints**

A similar approach will be used to describe and compare the proportion of subjects with reduction in HBV DNA < LLOQ, HBV DNA <LOD, HBV pgRNA <LLOQ and subjects with abnormal ALT at Baseline who have normal ALT for ABI-H0731+NrtI and PBO+NrtI.

Change in mean log10 HBV DNA and in mean log10 HBV pgRNA from Baseline for ABI-H0731+NrtI and PBO+NrtI will be compared using a linear model with Baseline values and stratification as covariates.

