## **10.7. Multiplicity Adjustment**

No formal inference is planned in this study. Hence no multiplicity adjustment is required.

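### Would the protocol's asymptotic 95% intervals, and its CMH test beside a no-inference statement, mislead on the primary efficacy result?

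*Combined protocol and SAP*

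**What the plan says.** Protocol Section 10.3.4 defines the endpoint: "The primary efficacy endpoint is the proportion of subjects with HBV DNA <LLOQ at Week 48". Each arm's proportion "will be reported along with the corresponding 95% asymptotic confidence interval by treatment group". The interval formula is not named. The section continues: "The proportion of responders will be compared between the 2 treatment groups using a" CMH test that accounts for the stratification factors. It names no effect measure and no interval for the difference.

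Section 10.3.5 extends this to secondary binary outcomes ("A similar approach will be used to describe and compare the proportion of subjects with reduction in HBV DNA" below LLOQ, and three others). It adds linear-model comparisons of change in log10 HBV DNA and log10 pgRNA.

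The Synopsis, under Statistical Methods, states "Due to sample size limitations, no formal statistical inference is planned" and then "Assessment of antiviral activity will be compared by treatment groups using 95% confidence intervals where appropriate". Section 10.7 says "No formal inference is planned in this study. Hence no multiplicity adjustment is required". Section 10.6 prescribes multiple imputation for missing primary-endpoint data. Section 6.1.1 plans 20 subjects per arm, and Section 10.1 says the sample size has no statistical basis. The opening of Section 10 leaves the full description of analyses to the SAP.

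The SAP, written on Amendment 1, reports in Section 1 that the sponsor ended the study early with 2 subjects randomized. Section 3 says that no statistical analysis will be done and only listings provided. Section 6 replaces the efficacy analysis with a listing of virology parameters.

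**The concern.** Three features of the protocol text look wrong together.

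- **Interval method.** If the asymptotic interval is Wald, it fails where the results could well lie. Subjects enter with HBV DNA above LLOQ on two screening samples despite more than 12 months of NrtI, so a low placebo rate is plausible. A high active rate is the hope.
- **Missing contrast.** The Synopsis promises a comparison by confidence intervals, but Section 10.3.4 supplies intervals within arms only. The effect of adding the drug, which is a primary objective, would have a p-value and no estimate with an interval.
- **Inference status.** Tests are prescribed in Sections 10.3.4 and 10.3.5, yet Section 10.7 sets multiplicity aside because there is no inference.

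In a completed 40-subject study, error bars could be too narrow near 0% or 100%, and an isolated p-value below 0.05 could be given more weight than the plan allows.

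**Working it through.** **The plan's own figure.** There is none to reproduce: 40 subjects is stated without power, alpha, effect size or interval width.

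**Inputs.** n = 20 per arm (Section 6.1.1), 95% level (Section 10.3.4), z = 1.96. The documents give no placebo rate for this population, so 1% to 20% is assumed. The active rates in Section 2.2.3.2.2 are indirect: 5/12 = 42% below LLOQ at Week 48 in treatment-naive subjects, and 21/26 = 81% and 13/14 = 93% with target not detected in already suppressed subjects (a different population and a stricter assay limit).

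**Wald interval**, p ± z√(p(1−p)/n):
- 0/20: 0 ± 0, zero width; 20/20 likewise.
- 1/20: 0.05 ± 1.96 × √(0.05 × 0.95/20) = 0.05 ± 0.096, or −4.6% to 14.6%.

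**Wilson interval at 0/20**: the upper limit is z²/(n + z²) = 3.84/23.84 = 16.1%. Clopper-Pearson gives 1 − 0.025^(1/20) = 16.8%.

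**Exact coverage** is the sum of the binomial probabilities of the counts whose interval contains the true rate. At 5%, Wald covers for counts 1 to 4: 0.377 + 0.189 + 0.060 + 0.013 = 63.9%. It misses 0/20, which has probability 0.95^20 = 35.8%. Wilson covers for counts 0 to 2: 0.358 + 0.377 + 0.189 = 92.5% (before rounding of the terms).

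| True rate | Wald | Wilson | Clopper-Pearson |
|---|---|---|---|
| 2% | 33.2% | 94.0% | 99.3% |
| 5% | 63.9% | 92.5% | 98.4% |
| 10% | 87.6% | 95.7% | 98.9% |
| 15% | 81.9% | 97.8% | 97.8% |
| 42% | 93.3% | 93.3% | 97.9% |
| 50% | 95.9% | 95.9% | 95.9% |
| 81% | 90.9% | 96.1% | 96.1% |
| 93% | 76.4% | 95.3% | 98.9% |

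The failure is therefore specific to Wald and largely to the extremes.

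**Count of p-values.** Section 10.3.5 names six comparisons (four binary, two linear). There are 13 visits from Week 2 to Week 48, so testing every comparison at every visit gives 6 × 13 = 78 p-values, and 78 × 0.05 = 3.9 below 0.05 under the null. This is an upper reading: Section 10.3.5 does not say which visits are compared; the every-visit reading comes from the endpoint list. The CMH test is also conservative at low rates. A simulation with four strata and 20 per arm put its size at 1.3% for a 5% rate and 3.9% for a 10% rate.

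**What the operative plan can produce.** With 2 subjects, whose allocation is not stated, no method helps:
- An arm with one subject has a Clopper-Pearson interval of 0 to 97.5% or 2.5% to 100%.
- Take one subject per arm, in the same stratum, with opposite outcomes. The CMH numerator is (1 − 0.5)² = 0.25 and the variance is 1·1·1·1/(2² × 1) = 0.25. Chi-square is 1.0 and p = 0.32, the most extreme result possible.
- If the two subjects are in different strata or in the same arm, the variance is zero and the statistic is undefined.

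The SAP accordingly drops both the interval and the test.

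**The case for a change.** The best argument for a change is that the protocol text is defective whatever happened later. Section 10.3.4 permits a method that breaks down at rates the design makes plausible. It offers no estimate with an interval for a primary objective, and it leaves its p-values unlabelled beside a statement that no inference is planned. Better wording would cost little.

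Much of that stands as a comment on drafting. Part of it does not:

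- Asymptotic does not name Wald, so the fault is an unnamed method, which the protocol left to the SAP.
- No section proposes judging the arms by whether their intervals overlap. That rule would have a null rate of 2(1 − Φ(1.96√2)) = 0.6% with equal standard errors, but it is not in the plan. The Synopsis can be read as promising between-group intervals.
- A nominal CMH p-value in a proof-of-concept study with no statistical sample size is consistent with Section 10.7; only the label is missing.
- The obvious remedy is not quite off the shelf. Section 10.6 requires multiple imputation, and Wilson, Clopper-Pearson and score-type difference intervals do not follow directly from the usual pooling of imputed proportions.

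The argument fails on consequence. The SAP does more than leave these points uncorrected: it removes every analysis to which they apply.

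**Conclusion.** No change is needed, because none would alter anything that will be reported. The arithmetic against a Wald interval is right: zero width at 0/20 and 20/20, and 64% coverage at an assumed 5% rate. But it describes a 20-per-arm analysis that will not take place. The study ended with 2 randomized subjects and a listings-only SAP, so the number of affected intervals, tests and p-values is zero.

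What remains is a protocol drafting point of the kind an analyst would settle when writing a full SAP: name the interval, state the between-arm contrast, and call the p-values descriptive. It would deserve attention only if this analysis text were reused in another study. The conclusion rests on the SAP being the operative analysis plan. It does not depend on the assumed placebo rate.

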### **10.3.5. Analysis of Secondary Efficacy Endpoints**

A similar approach will be used to describe and compare the proportion of subjects with reduction in HBV DNA < LLOQ, HBV DNA <LOD, HBV pgRNA <LLOQ and subjects with abnormal ALT at Baseline who have normal ALT for ABI-H0731+NrtI and PBO+NrtI.

Change in mean log10 HBV DNA and in mean log10 HBV pgRNA from Baseline for ABI-H0731+NrtI and PBO+NrtI will be compared using a linear model with Baseline values and stratification as covariates.

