**Secondary Endpoints:**

- Mean change in  $\log_{10}$  HBV DNA from Baseline at each timepoint
- Proportion of subjects with HBV DNA is <LLOQ at each timepoint
- Proportion of subjects with HBV DNA is <level of detection (target not detected) at each timepoint
- Mean change in  $\log_{10}$  HBV pgRNA from Baseline at each timepoint
- Proportion of subjects with HBV pgRNA <LLOQ at each timepoint
- Mean change in  $\log_{10}$  serum viral antigens (ie, HBeAg, HBcrAg, and HBsAg) from Baseline at each timepoint
- Proportion of subjects with abnormal ALT at Baseline who have normal ALT at each timepoint
- Analysis of ABI-H0731 and NrtI drug concentrations:
  - PK on study visit days of ABI-H0731 on ABI-H0731+NrtI
  - PK on study visit days of NrtI on PBO+NrtI and ABI-H0731+NrtI
- The incidence of HBV variants with reduced susceptibility to ABI-H0731

**Exploratory  
Endpoints:**

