**Table 5: HBV DNA for Virologically-Suppressed Subjects with CHB by Week of Treatment with ABI-H0731+NrtI (Study 201/211)**

Week of Treatment	HBV DNA Subjects with TND [n/N, (%)]	
	HBeAg Positive a (N=27)	HBeAg Negative a (N=16)
Baseline	2/27 (7)	10/16 (63)
Week 24	22/27 (81)	15/16 (94)
Week 48	21/26 (81)	13/14 (93)

Source: Study 211 Table 7

HBV DNA LOD=5 IU/mL.

Abbreviations: HBeAg = hepatitis B e antigen; HBV = hepatitis B virus; N=number of subjects in Intent-to-Treat population;

NrtI=nucleos(t)ide reverse transcriptase inhibitor of the HBV polymerase; TD=target detected; TND = target not detected.

a Subjects who received ABI-H0731+NrtI in Study 201

The virologically-suppressed subjects with CHB who enrolled in Study 201 had low HBV pgRNA at Baseline and so HBV pgRNA in this population is reported in Study 201 and Study 211 by a high sensitivity Assembly RT-qPCR assay with LLOQ <35 U/mL. [Table 6](#) summarizes the absolute value, change from Baseline in HBV pgRNA and proportion of subjects with HBV pgRNA <LLOQ by week of treatment. In HBeAg positive subjects, the mean (minimum, maximum) Baseline HBV pgRNA was 3.6 (1.5, 6.1) log10 IU/mL which decreased to 1.9 (1.5, 4.6) log10 IU/mL after 48 weeks, representing a mean (minimum, maximum) change of -1.7 (-3.7, 0) log10 IU/mL. Compared to HBeAg positive subjects, HBV pgRNA was lower in HBeAg negative subjects and showed less change over 48 weeks of treatment with ABI-H0731+NrtI. In HBeAg negative subjects, the mean (minimum, maximum) Baseline HBV pgRNA was 1.7 (1.5, 2.6) log10 IU/mL which decreased to 1.5 (1.5, 1.6) log10 IU/mL at

Protocol Amendment 1 ABI-H0731-205  
08 September 2020

Week 48. In both HBeAg positive and negative subjects, the proportion of subjects <LLOQ generally increased over time during treatment with ABI-H0731+NrtI.

**Table 6: HBV pgRNA for Virologically-Suppressed Subjects with CHB by Week of Treatment with ABI-H0731+NrtI (Study 201/211)**

Week of treatment	HBV pgRNA log 10 U/mL	
	HBeAg Positive a (N=27)	HBeAg Negative a (N=16)
Baseline		
n	27	16
Mean (min, max)	3.6 (1.5, 6.1)	1.7 (1.5, 2.6)
<LLOQ, n (%)	4 (15)	13 (81)
Week 12		
n	27	16
Mean (min, max)	1.9 (1.5, 3.7)	1.5 (1.5, 1.5)
Change from Baseline (min, max)	-1.7 (-3.5, 0)	-0.1 (-1.0, 0)
<LLOQ, n (%)	15 (56)	16 (100)
Week 24		
n	27	16

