## 4. STUDY PLAN

### 4.1. Study Design

This is a Phase 2a, multi-center, randomized, single-blind, PBO-controlled study, evaluating the safety, antiviral activity, and PK of ABI-H0731 administered in addition to standard of care NrtI in subjects with CHB who have not achieved adequate virologic suppression of HBV DNA <LLOQ on NrtI alone. For this study, HBV DNA is analyzed by COBAS TaqMan® Version 2.0 at the central laboratory (LLOQ=20 IU/mL).

The study will be conducted at approximately 10 study centers worldwide. Approximately 40 eligible subjects will be randomized in a 1:1 ratio to the treatment groups shown in the study overview presented in [Figure 4](#).

Study investigational drugs, ie, 300 mg (3×100 mg tablets) ABI-H0731 or matching PBO (3 tablets) and subjects' background NrtI therapy will be administered orally, once daily (QD). Group 1 will receive ABI-H0731+NrtI for 96 weeks, Group 2 will receive PBO+NrtI for 48 weeks followed by ABI-H0731+NrtI for 48 weeks until Week 96. All subjects will continue to receive NrtI alone during the 24-week follow-up period from Week 96 through Week 120.

Treatment assignments will be stratified by the concurrent NrtI administered (ie, ETV) versus tenofovir (alafenamide versus [TAF] or disoproxil fumarate [TDF]) and HBV DNA (HBV DNA ≥500 IU/mL versus <500 IU/mL) during the Screening visits. The study will enroll up to 75% subjects on ETV. Safety, antiviral activity, and PK will be assessed during treatment and the 24-week follow-up period.

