### 5.2. Inclusion Criteria

Subjects must meet all of the following inclusion criteria in order to be eligible for enrollment:

1. Willing and able to provide informed consent
2. Male or female between the ages 18 and 65 years (inclusive)
3. Body mass index (BMI) 18 to 36 kg/m^2 and a minimum body weight of 45 kg (inclusive)
4. Female subjects of child-bearing potential ([Appendix 4](#)) must be non-pregnant and have a negative serum pregnancy test at Screening and a negative urine pregnancy test predose on Day 1.
5. HBeAg positive or HBeAg negative CHB Chronic hepatitis B infection, defined as HBV infection documented for  $\geq 12$  months.
6. HBV DNA  $>LLOQ$  (using a commercially available assay with  $LLOQ=20$  IU/mL) from 2 samples drawn on 2 separate occasions during the Screening period approximately 10-14 days apart. If the results from these 2 samples indicate a decline in HBV DNA then a third sample will be collected at least a week later for Sponsor review and approval prior to randomization.
7. On a stable NrtI regimen (ETV, TDF, or TAF) for more than 12 months, without evidence of resistance and while known to be adherent to therapy
8. Lack of cirrhosis or advanced liver disease as documented by the following:
  - Liver biopsy results of METAVIR F0-F3 (absence of cirrhosis) within 1 year of Screening
  - OR
  - Fasting FibroScan®  $\leq 14$  kPa within 3 months of Screening (including the Screening visit) or other Sponsor-approved hepatic imaging method within 6 months of Screening indicating lack of cirrhosis (F0 to F3 or equivalent).

If the results from both liver biopsy and FibroScan are available, then the diagnostic method reporting the most advanced liver disease will be used to determine eligibility for the study.
9. Agreement to comply with protocol-specified contraceptive requirements (Refer to [Appendix 4](#)).
10. Agreement to abstain from alcohol abuse (defined as alcohol consumption exceeding 2 standard drinks per day on average (1 standard drink=14 grams of alcohol) and the use of illicit substances from Screening through the duration of the study

11. In good general health, except for CHB (in the opinion of the Investigator)
12. Have the ability to take oral medication and, in the opinion of the Investigator, be willing to adhere to study treatment

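### Does ignoring the assay floor in the secondary virology analyses understate the drug effect in this trial?

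*Combined protocol and SAP*

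**What the plan says.** Protocol Section 10.3.5 states that change in mean log10 HBV DNA and pgRNA, active against placebo, "will be compared using a linear model with Baseline values and stratification as covariates". Neither that section nor Section 10.6 says what value a result below the LLOQ takes; Section 10.6 deals only with missing data for the primary endpoint.

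Section 4.1 says HBV DNA is measured "at the central laboratory (LLOQ=20 IU/mL"). Inclusion criterion 6 requires HBV DNA above that limit "from 2 samples drawn on 2 separate occasions during the Screening period approximately 10-14 days apart" and sets no higher minimum. Randomization is stratified by HBV DNA "≥500 IU/mL versus <500 IU/mL) during the Screening visits", and by NrtI, but not by HBeAg status.

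The secondary endpoints include "Proportion of subjects with HBV pgRNA <LLOQ at each timepoint", and the exploratory endpoints include "Proportion of subjects with loss of serum viral antigens (defined as <LLOQ) in HBeAg, HBcrAg, and HBsAg". Neither is limited by baseline status. The ALT endpoint is: "Proportion of subjects with abnormal ALT at Baseline who have normal ALT at each timepoint".

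The SAP is based on Protocol Amendment 1. Its Section 1 reports early termination with 2 subjects randomized. Sections 3 and 6 replace statistical and efficacy analysis with by-subject listings. Sections 3.2.2 and 7.2 show laboratory values below the LLOQ as such.

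**The concern.** A drug meant to push HBV DNA below 20 IU/mL will, if it works, place many active-arm results at the floor. A subject who enters at 40 IU/mL can show a fall of at most 0.30 log10, whatever the drug does. An ordinary linear model treats the floor as a measurement, and adjusting for baseline does not undo the censoring. The estimated difference would then depend on how close subjects started to the floor as well as on the drug.

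The responder endpoints raise a separate question. A subject with pgRNA already below the LLOQ counts as a responder before the first dose, and an HBeAg-negative subject can meet the stated definition of HBeAg loss at baseline. The protocol's summary of the earlier extension study says "Compared to HBeAg positive subjects, HBV pgRNA was lower in HBeAg negative subjects and showed less change over 48 weeks", so the HBeAg mix would shape the pooled result. Had the planned analysis been run, these endpoints might have understated the depth of the antiviral effect.

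**Working it through.** **Figures in the documents.** The protocol gives no effect size, SD or power, so there is no design figure to reproduce. The floor is log10(20) = 1.30, matching the Table 3 footnote. In Table 6, 4/27 = 15% of HBeAg-positive and 13/16 = 81% of HBeAg-negative subjects had pgRNA below the LLOQ at baseline.

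**Largest observable HBV DNA fall**, with the floor taken as 20 IU/mL: log10(baseline/20).

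- 21 IU/mL: 0.02
- 40 IU/mL: 0.30
- 100 IU/mL: 0.70
- 500 IU/mL: 1.40

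**Planned model under the floor.** The simulation used 20 subjects per arm and 800 runs per scenario, with change regressed on arm, baseline and HBV DNA stratum. The assumptions, none of them from the documents, were: baseline log-uniform on 21–500 IU/mL in the low stratum and 500–10,000 IU/mL in the high stratum; SD 0.4 log10; a true fall of 0.1 log10 on placebo and 0.5, 1.0 or 2.0 on drug. Cells show estimated difference divided by true difference.

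| Share below 500 IU/mL | <LLOQ set to 20: fall 0.5 / 1.0 / 2.0 | <LLOQ set to 10: fall 0.5 / 1.0 / 2.0 |
|---|---|---|
| 25% | 0.94 / 0.90 / 0.77 | 0.98 / 0.95 / 0.85 |
| 50% | 0.87 / 0.80 / 0.62 | 0.96 / 0.89 / 0.72 |
| 75% | 0.82 / 0.70 / 0.47 | 0.93 / 0.84 / 0.59 |
| 100% | 0.75 / 0.59 / 0.34 | 0.91 / 0.78 / 0.48 |

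For example, with half the subjects below 500 IU/mL, a 1.0 log10 fall and substitution of 20, the true difference is −0.90 and the estimate −0.72: 0.72/0.90 = 0.80. Raising the upper baseline limit to 100,000 IU/mL moves no ratio by more than 0.03. The loss therefore runs from 1 − 0.98 = 2% to 1 − 0.34 = 66%. Power hardly moves: with substitution of 20 it is 0.77–0.85 with the floor against 0.81–0.87 without it for a 0.5 log10 fall, and about 1.00 either way for larger falls.

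**Would a censored model help?** A second simulation used within-subject SD 0.3, a true effect of −1.5 log10 and normal baselines truncated at the floor. With baseline mean 2.0 and SD 0.5, the linear model gave −0.68 and a left-censored (Tobit) model −1.58. With mean 3.0 and SD 1.0, they gave −1.22 and −1.50. The first case puts about 91% of subjects below 500 IU/mL. The data were generated from a normal model with a floor, so good recovery is largely built in, and the censored model still overshoots where censoring is heaviest.

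**pgRNA responders.** Let f be the HBeAg-negative share and assume the placebo arm does not change.

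- Below LLOQ at baseline: f × 13/16 + (1 − f) × 4/27
- Below LLOQ at Week 48: f × 13/14 + (1 − f) × 20/26
- Difference among subjects measurable at baseline: (Week 48 − baseline)/(1 − baseline)

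| f | Baseline | Week 48 | Difference, all | Difference, measurable |
|---|---|---|---|---|
| 30% | 35% | 82% | 47 points | 72 points |
| 50% | 48% | 85% | 37 points | 71 points |
| 70% | 61% | 88% | 27 points | 69 points |

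The arithmetic is sound but the population is not this one. Table 6 describes Study 201 subjects, who had to be at or below 20 IU/mL for at least 6 months before screening; this trial requires the opposite. In the viremic treatment-naive subjects of Study 202, none of 12 had pgRNA below the LLOQ at baseline, though by an assay with a higher LLOQ (135 against 35 U/mL). The true share here is unknown.

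**What the final analysis can contain.** The planned model has an intercept, arm, baseline and two stratification terms: 5 coefficients against 2 randomized subjects. Neither it nor a censored version can be fitted, and the SAP plans neither. Its Section 5.2 lists each subject's baseline HBeAg status and LLOQ group for HBV DNA, pgRNA and the antigens. Section 6 lists the virology results by visit.

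**The case for a change.** The best case for a change is that the protocol text is deficient and the repair is cheap. Section 10.3.5 has no LLOQ convention, and the background tables suggest that practice varied. In Table 6, all 16 HBeAg-negative subjects are below the LLOQ at Week 12, with mean, minimum and maximum of 1.5. That is log10(35) = 1.54 entered as a value, and so the convention with the larger loss. In Table 3 the HBV DNA minimum is 1.3 at Weeks 12 to 36 but 1.0 at Week 48, below the stated floor. HBeAg status is not a stratification factor, so chance imbalance among 40 subjects could also have mattered. The ALT endpoint shows that the authors knew how to restrict a denominator.

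Most of this stands as a description of the protocol. It does not show a marked understatement, since the loss could be trivial or large on inputs nobody has stated. The HBeAg part does not belong to the quoted model, which covers only HBV DNA and pgRNA; antigen change falls under the general descriptive summaries, and HBeAg loss and seroconversion are exploratory. Keeping subjects already below the LLOQ changes the population averaged over. It dilutes the effect without favouring an arm. Protocol Section 10 also left the full analysis description to a SAP, where a rule for such values normally sits. That SAP has been written and needs no substitution rule.

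**Conclusion.** No change follows, because there is nothing to gain. The omission in Section 10.3.5 is genuine, and had about 40 subjects been analysed it could have pulled the HBV DNA difference toward zero by 2% to 66% under the assumed scenarios. The primary endpoint would not have moved: every subject must screen above the LLOQ, and response is defined by falling below it, so no substituted value enters. The protocol plans no formal inference in any case.

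The deciding fact is in the SAP: 2 subjects, listings only, results below the LLOQ shown as such. No estimate will be produced that a censored model or a restricted denominator could correct, and a reader of the listings can see who started below the LLOQ or HBeAg negative. This rests on the SAP governing the final report, as it states. If Section 10.3.5 were reused for a trial that runs to completion, a stated rule for values below the LLOQ and baseline-based denominators would be worth adding there.
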